# **AMENDMENT HISTORY**

Version	Effective Date		Changes	Rationale
1.0	23-Jun-2022		Not Applicable	Initial release
2.0	06-Feb-2023	1.	General analysis definition summary section 2 has been updated to add (Table 1A) for visit windows.	1. The visit window is applied in order to have the new set of analysis visits based on the T&E schedule available in the protocol.
		2.	Clinical Laboratory Tests (section 6.2) has been updated for sensitivity analysis	2.Clinical Laboratory data was not captured prior to dose administration, so baseline definition is re-considered, used for sensitivity analysis (section 6.2).
		3.	Vital Sign and Physical Examination (section 6.3) has been updated to add Table 4 for Normal Ranges for Vital Signs	3.Normal Ranges for Vital Signs can provide sufficient information to describe the Abnormality results.
		4.	Progression-Free Survival (section 5.1.4) has been updated to add PFS analysis	4.PFS interpretation can provide sufficient information to describe the assessment criteria

#### **ABBREVIATIONS**

ADA anti-drug antibody ADR adverse Drug Reaction

AE adverse event

ATC anatomic and therapeutic Class

body mass index BMI body surface area **BSA** Bruton's Tyrosine Kinase **BTK** CI confidence interval CLtotal systemic clearance complete response CR **CRF** case report form **CSR** Clinical Study Report

dell 17p deletions in the short arm of chromosome 17

DMC Data Monitoring Committee

ECOG Eastern Cooperative Oncology Group

ECG electrocardiogram

eCRF electronic case report form eDC electronic data capture

EORTC QLQ C-30 European Organization for Research and Treatment of Cancer Quality of Life Questionnaires Core 30

EOT End-Of-Treatment

FDA Food and Drug Administration

FACIT Functional Assessment of Chronic Illness Therapy

GCP Good Clinical Practice

ICH International Conference on Harmonization

ICF Informed Consent Form/Document

IRB Institutional Review Board

IWCLL International Workshop on Chronic Lymphocytic Leukaemia

MCL Mantle Cell Lymphoma

MedDRA Medical Dictionary for Regulatory Activities

NCI-CTCAE National Cancer Institute Common Terminology Criteria for Adverse Events

PD preferred term
PI principal investigator
PR partial response

PRO Patient-Reported Outcome

PT preferred term
SAE serious adverse event
SAP Statistical Analysis Plan
SD standard deviation
SD stable disease

SMQsSLL Standardised MedDRA queries Small Lymphocytic Lymphoma

SOC system organ class

TEAE treatment-emergent adverse event
US NCI United States National Cancer Institute

WHO World Health Organization

WHO-DD World Health Organization Drug Dictionary

#### 1. INTRODUCTION

Ibrutinib (PCI-32765; JNJ-54179060) is a first in class potent, orally administered, covalently binding small molecule inhibitor of Bruton's tyrosine kinase (BTK) currently under development for the treatment of B-cell malignancies.

This study is designed to assess the safety of ImbruvicaTM (ibrutinib capsule 140 mg) prescribed as per locally approved prescribing information in Indian patients of chronic lymphocytic leukemia (CLL) or mantle cell lymphoma (MCL) who have received at least one prior therapy or CLL with 17p deletion.

This statistical analysis plan (SAP) for the 54179060LYM4005 describes the statistical analysis for subject information, safety data and clinical response.

# 1.1. Trial Objectives

#### **Primary Objective**

The primary objective of this study is to evaluate the safety of ImbruvicaTM (ibrutinib capsule 140 mg) under actual conditions of use, and to understand the Incidence of adverse events (AEs) (Serious and Non-serious AEs).

# **Exploratory Objectives**

To analyse the following outcomes with ibrutinib:

- Baseline patient and disease characteristics
- Response assessment and progression criteria as per International Workshop on Chronic Lymphocytic Leukaemia (IWCLL) criteria for CLL and revised response criteria for malignant lymphoma for MCL.
- Change in patient reported outcomes as measured by
  - Quality of Life by EORTC QLQ C-30 instrument (European Organization for Research and Treatment of Cancer Quality of Life Questionnaires Core 30)
  - Fatigue by FACIT Fatigue instrument (Functional Assessment of Chronic Illness Therapy Fatigue)

# 1.2. Trial Design

This is a prospective open label, single arm, multicenter, phase IV interventional study to describe the safety of ImbruvicaTM in Indian subjects. Approximately, 75 subjects selected by investigators and determined to be eligible for ibrutinib treatment as per protocol eligibility criteria will be enrolled in the study.

The recommended dose of Imbruvica $^{TM}$  as per the locally approved prescribing information is 420 mg (three 140 mg capsules) as a single daily dose for CLL and 560 mg (four 140 mg capsules) as a single daily dose for MCL.

# **Screening cum Enrolment Visit (Day 1)**

Prior to data collection, all subjects [and/or their legally acceptable representative where applicable] must sign an informed consent form (ICF) allowing data collection and source data verification in accordance with local regulations. Data collected at this visit may include but not limited to demographics, medical history, disease related history, concomitant medications, patient-reported outcomes (PROs), laboratory investigations, etc.

# **Treatment Period (Visits 1 to 6 and Visit 7)**

Enrolled subjects will be followed up to 12 months from the treatment initiation. During the study period, data will be collected at monthly intervals for the first 6 months, (monthly visit  $\pm$  7 days; Visits 1 to 6). Subsequent visit would be at 9 months  $\pm$  7 days [Visit 7].

#### **End-of-Treatment (EOT) (Visit 8)**

The End-of-Treatment (EOT) visit will be conducted after the completion of 12-months ImbruvicaTM treatment (at Visit 8) or on the day at which the patient discontinued the ImbruvicaTM treatment or study.

[figure not shown]
The end of the treatment will be the End of Treatment visit within the study for the last participating patient.

#### Follow up period (End of Study)

A telephonic follow-up will be conducted 30 days after the EOT Visit.

The observation period including the Enrolment Visit and telephonic Follow-up will be up to a maximum duration of 13 months for each patient.

#### **Schematic Overview of the study**

The overall duration of the study, including recruitment [and/or follow up], is expected to be 36 months.

# 1.3. Statistical Hypotheses for Trial Objectives

No formal hypothesis testing will be conducted. Data will be summarized using descriptive statistics. Continuous variables will be summarized using the number of observations, mean, SD, median, and range as appropriate. Categorical values will be summarized using the number of observations and percentages as appropriate. Exploratory endpoints will be summarized using descriptive statistics.

# 1.4. Sample Size Justification

The primary objective of this study is to estimate the incidence of AEs in Indian subjects under actual conditions of use of ImbruvicaTM. A sample size of 75 subjects is as per the recommendations of Subject Expert Committee (Oncology & Hematology) made in its 70th meeting held on 23rd May 2018 at Central Drugs Standard Control Organization HQ, New Delhi communicated vide F.N. 12-10/2017-DC (Pt-Johnson-snd).

# 1.5. Randomization and Blinding

Randomization and blinding will not be applicable for this study as this is a single arm, open label study.

Participating sites will be encouraged to enroll subjects in a consecutive manner when subjects come for their regular consultation to minimize bias in patient selection.

#### 2. GENERAL ANALYSIS DEFINITIONS

The below mentioned general principles will be followed throughout the study:

- The change from baseline is defined as the post-baseline value minus the baseline value. Definition of baseline is provided in section 2.3.
- Descriptive statistics will include number of non-missing subject (n), mean, median, standard deviation (SD), minimum and maximum values for continuous variables, and for categorical variables the frequencies and percentages of subjects will be presented.
- For continuous data, mean and median will be rounded to 1 decimal place more than original data, SD will be rounded to 2 decimal places more than original data and minimum and maximum will be displayed with the same precision as the original data.
- For categorical data, percentages will be rounded to 1 decimal place.
- If a count is 0, the percentage (0%) should not be displayed. The 0 count will be displayed, but the corresponding percentage should be omitted.
- All study data will be included in study data listings. In general, all data will be listed by time point within subject.
- In general, missing data will not be imputed.
- SAS® version 9.4 will be used for all analyses.
- Visit Windows for PRO analysis:

To allow for variation in scheduling, the following set of visit windows will be used to assign evaluations to a most appropriate visit for analysis (Avisit).

Table 1A:

Visit	Avisit	Start Day	Target Day	End Day
SCR/Enrollment visit/Month 1	Screening	-	1	1
Visit 1/ Month 2 (end of month 1)	Month 1	2	30	37
Visit 2/Month 3 (end of month 2)	Month 2	38	60	67
Visit 3/Month 4 (end of month 3)	Month 3	68	90	97
Visit 4/ Month 5 (end of month 4)	Month 4	98	120	127
Visit 5/ Month 6 (end of month 5)	Month 5	128	150	157
Visit 6/ Month 7 (end of month 6)	Month 6	158	180	187
Visit 7/ Month 10 (end of month 9)	Month 9	188	270	277
Visit 8 (end of month 12/End of Treatment)	Month 12	278	360	367

8

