#### **Exploratory Endpoints**

- Proportion of participants experiencing clinical response as per assessment criteria defined in section 9.1
- Change from baseline in patient-reported outcomes as per EORTC QLQ C-30 and FACIT Fatigue

The safety analysis population will include all subjects who sign the ICF and receive at least one dose of ImbruvicaTM. The verbatim terms used by participating physicians to document AEs in the CRF will be coded using the Medical Dictionary for Regulatory Activities (MedDRA). For each adverse event, the percentage of subjects who experience at least 1 occurrence of the given event will be summarized. Adverse events and serious adverse events will be summarized for the study duration by body system, preferred term, intensity, and relationship to ImbruvicaTM using descriptive statistics. Where appropriate, additional summaries, listings, or narratives may be provided for any deaths, serious adverse events, or any adverse events of clinical interest. Changes from baseline to the worst AE grade experienced by a patient during the study will be provided as shift tables. Results of investigations data including vital signs, if any, will be summarized using descriptive statistics.

All subjects who have received at least one dose of ImbruvicaTM and have completed one post-treatment PRO assessment will be considered for exploratory analysis. Exploratory endpoints will be summarized using descriptive statistics. Shift tables will be provided to determine the change in reported outcomes from baseline (Enrolment Visit) until Visit 8 /EOT.

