## **Observation Visits (Visit 1 to Visit 8)**

The subjects will be followed up at every monthly interval during Visit 1 to Visit 6 for the first 6 months, followed by seventh visit at month 9 and eighth visit at month 12, and as outlined in the TIME AND EVENTS SCHEDULE The below mentioned procedure and measurements will be performed

- Current medical history (symptoms & signs if any, physical examination including vitals)
- Disease progression assessment
- Compliance Assessment
- Patient-completed PRO instruments (questionnaires and scales)
  - o FACIT Fatigue Instrument
  - o EORTC QLQ-30
- Type, dosage and duration of concomitant medication
- AEs for ImbruvicaTM (see Section
- Investigations (Hematology and coagulation profile); as per TIME AND EVENTS SCHEDULE.

**Note:** Visit 8 or discontinuation visit will be the EOT Visit.

A discontinuation visit is the visit at which the participating physician is discontinuing ImbruvicaTM or first routine clinic visit after the patient stopped taking ImbruvicaTM on his own.

At the discontinuation visit, information on date and reason(s) for ImbruvicaTM discontinuation will be collected, if available. The data for discontinuation visit will be collected on the EOT Visit page in CRF.

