## **Dosing Schedule**

Enrolled subjects will receive ibrutinib treatment for the duration of 12 months or till EOT visit. Each subject will receive a monthly supply (90 capsules for CLL and 120 capsules for MCL) at the enrolment visit till month 6. Subsequent refill will be provided at the end of the month or after consumption of the dose provided. Sufficient dose for subsequent 3 months will be provided at the beginning of month 7 and month 10.

	Enrolment visit (beginnin g of month 1)	Mont h 2	Mont h 3	Mont h 4	Mont h 5	Mont h 6	Mont h 7	Mont h 8	Mont h 9	Mont h 10	Mont h 11	Mont h 12
Ibrutini b monthly refill	X	X	X	X	X	X	X X X			2	ζ	

The following data will be documented during the study period:

- Indication for ImbruvicaTM
- Start/stop dates and reason for initiation/discontinuation of ImbruvicaTM
- Date and reason for dose reductions. If dosage reduction of ImbruvicaTM is needed, the decision will be taken as per participating physician's discretion and it should be based on and consistent with the recommendation given in the locally approved Prescribing Information.

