#### 2.2. Study Day and Relative Day

Study Day 1 or Day 1 refers to the start of the first study agent administration. All safety assessments at all visits will be assigned a day relative to this date.

Study day or relative day for a visit is defined as:

- Visit date (date of Study Day 1) +1, if visit date is ≥date of Day 1
- Visit date Date of Day 1, if visit date <date of Day 1

There is no 'Day 0'.

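### SAP Table 1A's PRO windows run 82 days early but only 7 days late at Months 9 and 12, so late questionnaires take the next visit's label and none after Day 367 has an analysis visit

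*SAP*

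**What the plan says.** SAP section 2 (General Analysis Definitions) sets visit windows for the PRO analysis only. It states that "the following set of visit windows will be used to assign evaluations to a most appropriate visit for analysis (Avisit"), and Table 1A gives a start, target and end day for each analysis visit. The two long intervals are the rows "Visit 7/ Month 10 (end of month 9"), Day 188 to 277 with target 270, and "Visit 8 (end of month 12/End of Treatment"), Day 278 to 367 with target 360. The latter is the last row.

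Days are counted as in SAP section 2.2: "Study Day 1 or Day 1 refers to the start of the first study agent administration", with no Day 0. SAP section 2 also says that "All study data will be included in study data listings", so a questionnaire without an analysis visit would still be listed.

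The protocol (Synopsis, section 3.1 and Time and Events Schedule) allows ±7 days around monthly visits to Month 6, then Month 9 and Month 12. It does not define a month in days. Section 5 (Observation Visits) says that "Visit 8 or discontinuation visit will be the EOT Visit". The EOT visit therefore falls early for a subject who stops early. For PROs, the Synopsis says: "Shift tables will be provided to determine the change in reported outcomes from baseline (Enrolment Visit) until Visit 8 /EOT".

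**The concern.** An analysis window should send a questionnaire to the visit it best represents. Table 1A follows the protocol's +7-day limit on the late side and gives all the remaining time to the next visit. Where visits are a month apart the distortion is small. Where they are three months apart, a slightly late visit is labelled as one due almost three months later.

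Four consequences follow for change from baseline in QLQ-C30 and FACIT Fatigue:

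- The Month 9 and Month 12 summaries can mix scores taken near target with scores up to 82 days earlier.
- A late Month 6 form (Day 188) and a proper Month 9 form (Day 270) fall in the same window, and the SAP does not say which to use.
- A Month 12 form after Day 367 is left out of the by-visit summaries.
- An early EOT form goes to whichever window its study day falls in, alongside scheduled visits. Alternatively, if the words End of Treatment in the last row override study day, it goes to Month 12. The SAP does not say which, so two programmers could produce different tables from the same data.

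**Working it through.** **Inputs.** From SAP Table 1A, as start/target/end: Month 1 2/30/37; Month 2 38/60/67; Month 3 68/90/97; Month 4 98/120/127; Month 5 128/150/157; Month 6 158/180/187; Month 9 188/270/277; Month 12 278/360/367. From the protocol: tolerance ±7 days. From SAP 2.2: first dose is Day 1.

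**Step 1. How the table is built.** End minus target is 7 in all eight rows (for example 187 − 180, 277 − 270, 367 − 360). Each start is the previous end plus 1. Target minus start:

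| Visit | Days before target | Days after target |
|---|---|---|
| Month 1 | 30 − 2 = 28 | 7 |
| Months 2 to 6 | 22 each | 7 |
| Month 9 | 270 − 188 = 82 | 7 |
| Month 12 | 360 − 278 = 82 | 7 |

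**Step 2. The boundary days.**

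- Day 188: 188 − 180 = 8 days after the Month 6 target and 82 before the Month 9 target; assigned to Month 9.
- Day 278: 278 − 270 = 8 days after the Month 9 target and 82 before the Month 12 target; assigned to Month 12.
- Day 368: 8 days after the Month 12 target; assigned to nothing.

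**Step 3. Days strictly nearer another post-baseline target.** These are Days 38-44, 68-74, 98-104, 128-134 and 158-164 (5 × 7 = 35), Days 188-224 (37) and Days 278-314 (37). The total is 35 + 37 + 37 = 109 of the 366 days from Day 2 to Day 367. Days 45, 75, 105, 135, 165, 225 and 315 are ties, which makes 116 with them.

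**Step 4. Distance inside the long windows.** More than 7 days before target: Days 188-262 in Month 9 and Days 278-352 in Month 12, which is 75 of 90 days in each. Steps 3 and 4 count calendar days, not questionnaires.

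**Step 5. Visits inside the protocol's ±7 days.** Assumption: visits are spread evenly over the 15 days from −7 to +7. The result then depends on how sites book, which the documents do not state.

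| Booking | Month 6 labelled Month 9 | Month 9 labelled Month 12 | Month 12 without a label |
|---|---|---|---|
| On study Day 30n (Table 1A targets) | 0 of 15 | 0 of 15 | 0 of 15 |
| 30n days after first dose (study Day 30n + 1) | 1 of 15 (Day 188) | 1 of 15 (Day 278) | 1 of 15 (Day 368) |
| By calendar month | 24.4% | 33.3% | 42.2% |

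The second row arises because there is no Day 0: 180 days after first dose is Day 181, and 181 + 7 = 188. The same 1 in 15 applies at Months 1 to 5.

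The third row averages over all start dates in 2019-2021. That date range is a further assumption, because the documents give no enrolment dates. Six calendar months fall on Day 182-185, so 2 to 5 of the 15 days pass Day 187. Nine months fall on Day 274-277, so 4 to 7 pass Day 277. Twelve months fall on Day 366, or Day 367 across a leap day, so 6 or 7 pass Day 367.

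**Step 6. The same check with nearest-target windows.** With the limits given under the fix, 0 of 15 days are misassigned or unassigned at every visit, under all three booking rules.

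**The case against.** The strongest reply is that the table respects the protocol's tolerance. On Table 1A's own targets, Days 188, 278 and 368 are each one day outside ±7, so no visit on schedule is moved. The SAP's Amendment History says the windows were based on the protocol's schedule. The drug supply also points to 30-day months: "Each subject will receive a monthly supply (90 capsules for CLL and 120 capsules for MCL"), at 3 and 4 capsules a day, lasts 30 days. The 24% to 42% figures need calendar-month booking, an even spread and assumed start dates. The counts of 109 and 75 of 90 are days on which few questionnaires are planned. Visit 8 and EOT are already paired in both documents, which suggests that early EOT forms belong with Visit 8. The endpoints are exploratory and descriptive, and late forms are still listed.

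Much of this stands. The effect may be nil if sites book exactly on Table 1A's targets, the number of affected records cannot be estimated from the documents, and the consequences are confined to exploratory summaries.

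It does not rescue the rule. The SAP introduces the windows to allow for variation in scheduling, so an 8-day-late visit is just what they must handle, and it goes to a target 82 days away. Booking 30 days from first dose is consistent with the drug supply and already puts a +7 visit into the wrong window. No statement lets the nominal visit override study day, and none covers two records in one window. The pairing of Visit 8 with EOT suggests an intention but does not settle it.

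**Conclusion.** The concern holds. Table 1A does not meet its own aim for visits that run late. The fault is largest at the Month 6/Month 9 and Month 9/Month 12 boundaries and at the Day 367 cut-off. The table arithmetic is certain. The share of in-tolerance visits affected ranges from 0% to 42%, depending on the booking practice and the assumptions in the working. Visits outside tolerance and early EOT forms come on top of that, in numbers the documents do not give.

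The change should be made, but it is not critical: it affects the by-visit summaries of QLQ-C30 and FACIT Fatigue, which are exploratory and descriptive. The primary adverse-event endpoint is untouched.

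**What to change.** Replace the limits in Table 1A by nearest-target windows on the same targets, with ties going to the earlier visit:

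| Analysis visit | Window (study day) |
|---|---|
| Month 1 | 2-45 |
| Month 2 | 46-75 |
| Month 3 | 76-105 |
| Month 4 | 106-135 |
| Month 5 | 136-165 |
| Month 6 | 166-225 |
| Month 9 | 226-315 |
| Month 12 | 316 up to the Visit 8/EOT visit, with no Day 367 cut-off |

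Add two sentences. First, if a window holds more than one record, use the one nearest the target. Second, in by-visit summaries, show the EOT assessments of subjects who stop early in a separate EOT row, and keep them in the protocol's shift table from baseline to Visit 8/EOT, so that analysis does not change. The separate row is a presentation choice and can be decided independently, provided the SAP states where early EOT forms go.

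The cost is one table, two sentences and a re-run of the PRO outputs, with no new data. In the closed windows from Month 2 on, an assessment may still lie up to 45 days from its target, against 82 now, and the separate EOT row lowers the n in some by-visit cells.

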# 3.1. Overview of Study Design

Relapsed/refractory CLL and MCL patients who have received at least one therapy or CLL patients with deletion 17p selected by investigators and determined to be eligible for ibrutinib treatment as per protocol eligibility criteria will be enrolled in the study. Each subject will receive ibrutinib treatment for a period of 12 months or till disease progression, whichever is earlier. Enrolled subjects will be followed up to 12 months from the treatment initiation. During the study period, data will be collected at monthly intervals for the first 6 months, (monthly visit  $\pm$  7 days; Visit 1 to 6). Subsequent visit would be at 9 months  $\pm$  7 days [Visit 7]. The End-of-Treatment (EOT) visit will be conducted after the completion of 12-months ImbruvicaTM treatment (at Visit 8) or on the day at which the patient discontinued the ImbruvicaTM treatment or study. A telephonic follow-up will be conducted 30 days after the EOT Visit.

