# 10. SUBJECT COMPLETION/DISCONTINUATION OF STUDY TREATMENT/ WITHDRAWAL FROM THE STUDY

#### 10.1. Completion

The study will be considered completed with the EOS within the study for the last patient participating in the study. A subject will be considered to have completed the study if he or she has completed the telephonic assessments at month 13.

Last completed assessment of subjects who prematurely discontinue study treatment for any reason before completion of this phase IV study will be considered for analysis.

The sponsor reserves the right to close a participating site for data collection or to terminate the study at any time for any reason at the sole discretion of the sponsor. A participating site is considered closed when all required documents and study specific supplies have been collected and a site closure assessment has been performed.

The participating physician may initiate site closure at any time, provided there is reasonable cause and sufficient notice is given in advance of the intended termination.

Reasons for the early closure of a participating site by the sponsor or participating physician may include but are not limited to:

- Failure of the participating physician to comply with the protocol, requirements of the IRB or local health authorities, or the sponsor's procedures, or GCP guidelines;
- Inadequate recruitment of subjects by the participating physician.

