# 2.3. Baseline and Endpoint

Baseline is defined as the last non-missing observation on or prior to the start of the first study agent administration.

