#### **Exploratory Endpoints**

- Proportion of subjects experiencing clinical response as per assessment criteria defined in section 9.1 of the protocol.
- Change from baseline in patient-reported outcomes as per EORTC QLQ C-30 and FACIT Fatigue

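### The SAP's day-based PRO windows place an early end-of-treatment questionnaire in a calendar month, and no readable SAP text delivers the protocol's change from baseline to Visit 8/EOT

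*SAP*

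**What the plan says.** **Protocol.** The synopsis, under Exploratory Endpoints, plans the PRO analysis as follows: "Shift tables will be provided to determine the change in reported outcomes from baseline (Enrolment Visit) until Visit 8 /EOT". Section 3.1 places the EOT visit after 12 months of treatment "or on the day at which the patient discontinued the" drug or left the study. Section 5 (Observation Visits) treats a discontinuation visit as the EOT visit and records it on the EOT page of the CRF. The Time and Events Schedule has a combined Visit 8/End of Treatment column with both questionnaires, and none at the telephone follow-up. Section 10.1 adds a general rule: "Last completed assessment of subjects who prematurely discontinue study treatment for any reason before completion of this phase IV study will be considered for analysis".

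**SAP.** Section 2 says that "the following set of visit windows will be used to assign evaluations to a most appropriate visit for analysis (Avisit", and Table 1A gives start, target and end days. Its last row is labelled "Visit 8 (end of month 12/End of Treatment"), has the analysis visit Month 12, and runs from Day 278 to Day 367 with target Day 360. The same section says: "In general, missing data will not be imputed". Section 2.3, titled Baseline and Endpoint, fixes the reference value ("Baseline is defined as the last non-missing observation on or prior to the start of the first study agent administration") and lists the PRO endpoint as "Change from baseline in patient-reported outcomes as per EORTC QLQ C-30 and FACIT Fatigue", with no time point.

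**The concern.** The protocol's Visit 8/EOT column gives each subject one final questionnaire, whether it comes at month 12 or earlier. Read by day, Table 1A scatters the early ones over the calendar months, and nothing in the readable SAP gathers them again.

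The gap cannot close later. Under protocol Section 4, a subject who stops early has EOT assessments and then the follow-up 30 days afterwards, which carries no questionnaire. A subject whose EOT falls before Day 278 therefore has no later scheduled form that could enter Month 12.

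Protocol Section 4 names physician-judged safety and disease progression as the grounds for stopping. Absence from Month 12 may therefore be related to how the subject felt. A reader who takes the last column as the change over treatment would be reading a selected group, while the protocol's own summary that includes early leavers would not exist.

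**Working it through.** **Step 1. Where does an EOT form land?** Every window after screening ends 7 days after its target and starts the day after the previous window ends. Applying the Table 1A days:

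| EOT study day | Analysis visit |
|---|---|
| 20 | Month 1 |
| 45 | Month 2 |
| 100 | Month 4 |
| 150 | Month 5 |
| 200, 240, 277 | Month 9 |
| 278, 300, 367 | Month 12 |
| 368, 372 | none |

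An EOT before Day 278 goes to Month 1-6 or Month 9. An EOT on Days 278-367 goes to Month 12 even if the drug was stopped early. A Visit 8 at 365 + 7 = 372 days has no window. The SAP also gives no rule for two forms in one window, which an early EOT soon after a scheduled visit would create.

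**Step 2. Label against day.** By label, a Day 45 EOT form belongs in the End of Treatment row and would be tabulated as Month 12. By day, it is Month 2. The SAP does not resolve this. Its rule assigns evaluations by window, which favours day.

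**Step 3. How many subjects might be affected?** The documents give no dropout assumption and no CLL/MCL split. The sample size of 75 follows a committee recommendation, so there is no planned figure to reproduce. The inputs below are background figures from protocol Section 1.2, used only for scale:

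- CLL 12-month PFS of 88%, from the relapsed/refractory 420 mg group. The 82% beside it is the 840 mg group, so it is not used.
- MCL 6-month PFS of 63%.
- Discontinuation for adverse events of 11.8%, with median treatment of 8.3 months in the pooled data.

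Assumptions: constant hazards; progression or death ends treatment; CLL share of 50-90%; a month of 30.4375 days; the 11.8% accrues over 8.3 months, independently of progression.

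- CLL progression-free at Day 278: 0.88^(278/365.25) = 0.907
- MCL progression-free at Day 278: 0.63^(278/182.625) = 0.495
- No adverse-event discontinuation by Day 278: 0.882^(278/252.6) = 0.871

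| CLL share | On drug, PFS only | Off drug | On drug, with AE stops | Off drug |
|---|---|---|---|---|
| 90% | 75 × (0.9×0.907 + 0.1×0.495) = 65.0 | 10.0 (13%) | 65.0 × 0.871 = 56.6 | 18.4 (25%) |
| 50% | 75 × (0.5×0.907 + 0.5×0.495) = 52.6 | 22.4 (30%) | 52.6 × 0.871 = 45.8 | 29.2 (39%) |

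These shares only approximate absence from Month 12. Some subjects on drug will miss a form, and some who stopped shortly before Day 278 may have their discontinuation visit after it.

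**Step 4. What would that do to a mean?** With f the share absent from Month 12, and every subject supplying an EOT form:

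Month 12 mean − all-subject EOT mean = f × (mean change of those present − mean change of those absent).

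The documents give no value for the bracket. If it is zero, the difference is zero. For scale, protocol Section 9.1 calls 10 points clinically meaningful on the QLQ-C30 functioning scales. A 10-point discrepancy would need a gap of 10/0.39 = 26 points at the highest share and 10/0.13 = 77 points at the lowest.

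**The case against.** **The row is labelled End of Treatment.** One can argue that the SAP meant early EOT forms to go there. The ambiguity is real, so a reader might infer too much in calling this a deliberate exclusion. But the label reading would put a Day 45 form in a column headed Month 12, so both readings need correction.

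**Month 12 is not confined to subjects still on drug.** A reader might infer that it is. The documents do not support this. A subject who stops on Day 290 and completes the EOT form counts in Month 12. Protocol Section 5 also lets the discontinuation visit be the first routine visit after the subject stopped. The group is defined by having a form on Days 278-367.

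**The protocol text is looser than it looks.** Section 10.1 is not specific to PROs, and summarising a Day 100 form under Month 4 does consider it for analysis. In the synopsis, until Visit 8/EOT could mean tables by visit up to the end. Section 10.1 is therefore only weak support. The synopsis sentence is stronger: it names shift tables and Visit 8/EOT together, and no readable SAP text plans a PRO shift table.

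**Attrition will be partly visible.** Early forms are not lost; they appear in the monthly summaries and listings. Non-missing counts, disposition with reasons (SAP Section 4.2) and PFS at 6 and 12 months (Section 5.1.4) are planned. This stands, although none of these gives the change to EOT.

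**Figures are missing from SAP Section 5.1.2.** At least one appears to be the FACIT item list. The absence of a rule can be stated only for the readable text.

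**Conclusion.** The point holds as a gap between protocol and SAP. Following the day windows as written leaves the protocol's change to Visit 8/EOT undelivered, and the label of the last row contradicts its day range for an early EOT. The Month 12 change omits subjects whose EOT form falls before Day 278.

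The scale is illustrative: about 10-22 of 75 subjects off drug by then from progression or death alone, and about 18-29 with adverse-event stops added. The second range may be too high, since fatal adverse events can be counted twice.

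A reader might infer that mean quality of life will look better over time, or attach a number of points to the bias. The documents support neither. The gap between leavers and stayers is unknown in size and sign, and subjects who die or are lost may have no EOT form at all.

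The endpoint is exploratory and descriptive. No test, sample size or primary safety result depends on it. Priority is low to moderate.

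**What to change.** 1. State in SAP Section 2 that the day windows govern the by-month PRO tables, and remove End of Treatment from the Month 12 label.
2. Add a separate derived analysis visit, Visit 8/EOT: the Visit 8 questionnaire or, if treatment stopped early, the discontinuation-visit questionnaire, whatever the study day.
3. Produce the change and shift tables from baseline to Visit 8/EOT on it, as a supplement to the monthly tables.
4. Show the number contributing and the number still on treatment at each month.
5. If the last post-baseline form is used where no EOT form exists, label that table a last-observation summary, because the SAP generally does not impute.

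The cost is one derivation and one extra set of tables, with no new data. The drawback is that Visit 8/EOT mixes different times on treatment, which is why it should not replace the monthly tables.
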